9.5. Pharmacokinetics

At the times specified in the Schedule of Activities (Section 2), venous blood samples of approximately 3 mL each will be collected. PK samples will not be analyzed for ixekizumab serum concentration unless ADA samples are also analyzed due to hypersensitivity or other adverse events, as described in Section 9.6.1.

Samples will be retained for a maximum of 1 year after the last subject visit.

9.6. Pharmacodynamics

Not applicable.

9.6.1. Immunogenicity Assessments

At the visits and times specified in the Schedule of Activities (Section 2), venous blood samples of approximately 10 mL each will be collected to determine antibody production against ixekizumab. Due to the crossover design ADA samples will be collected and not analyzed unless clinically suggested by hypersensitivity or other AEs.

In the event of drug hypersensitivity reactions (immediate or non-immediate), additional samples will be collected as close to the onset of the event as possible, at the resolution of the event, and at least 30 days following the event. Instructions for the collection and handling of blood samples will be provided by the sponsor. The actual date and time (24-hour clock time) of each sampling will be recorded.

Samples will be retained for a maximum of 15 years after the last subject visit, or for a shorter period if local regulations and ERBs allow, at a facility selected by the sponsor. The duration allows the sponsor to respond to future regulatory requests related to ixekizumab. Any samples remaining after 15 years will be destroyed.

9.7. Genetics

A blood sample will be collected for pharmacogenetic analysis as specified in the Schedule of Activities, where local regulations allow.

Samples will not be used to conduct unspecified disease or population genetic research either now or in the future. Samples will be used to investigate variable exposure or response to

ixekizumab and to investigate genetic variants thought to play a role in Ps. Assessment of variable response may include evaluation of AEs or differences in efficacy.

All samples will be coded with the subject number. These samples and any data generated can be linked back to the subject only by the investigative site personnel.

Samples will be retained for a maximum of 15 years after the last subject visit, or for a shorter period if local regulations and/or ERBs impose shorter time limits, for the study at a facility selected by Lilly or its designee. This retention period enables use of new technologies, response to regulatory questions, and investigation of variable response that may not be observed until later in the development of ixekizumab.

Molecular technologies are expected to improve during the 15 year storage period and therefore cannot be specifically named. However, existing approaches include whole genome or exome sequencing, genome wide association studies, multiplex assays, and candidate gene studies. Regardless of technology utilized, data generated will be used only for the specific research scope described in this section.

9.8. Biomarkers

Not applicable.

9.9. Health Economics

Not applicable.

10. Statistical Considerations and Data Analysis

10.1. Sample Size Determination

Up to 102 subjects may be enrolled to maximize the intent to have 78 subjects (26 subjects per treatment sequence) complete the study.

The objective of this study is to evaluate the injection pain immediately following dosing. Because of the crossover study design, each subject will have the opportunity to receive each treatment.

Subjects who are randomized but not administered treatment may be replaced to ensure that approximately 78 subjects may complete the study.

10.2. Populations for Analyses

10.2.1. Study Participant Disposition

A detailed description of subject disposition will be provided at the end of the study.

10.2.2. Study Participant Characteristics

The subjects' age, sex, weight, height, BMI, race, and other demographic characteristics will be recorded and summarized using descriptive statistics.

10.3. Statistical Analyses

Statistical analysis of this study will be the responsibility of Eli Lilly and Company or its designee.

Safety analyses will be conducted for all enrolled subjects who receive at least 1 dose of study drug, whether or not they completed all protocol requirements.

Continuous data will be summarized in terms of the mean, standard deviation, minimum, maximum, median, and number of observations. Categorical data will be summarized as frequency counts and percentages.

Any change to the data analysis methods described in the protocol, and the justification for making the change, will be described in the clinical study report. Additional exploratory analyses of the data will be conducted as deemed appropriate. Complete details of the planned analyses will be documented in the Statistical Analysis Plan.

10.3.1. Safety Analyses

10.3.1.1. Clinical Evaluation of Safety

All IP and protocol procedure AEs will be listed, and if the frequency of events allows, safety data will be summarized.

The incidence of symptoms for each treatment will be presented by severity and by association with IP as perceived by the investigator. Symptoms reported to occur prior to study entry will be distinguished from those reported as new or increased in severity during the study. Each symptom will be classified by the most suitable term from the medical regulatory dictionary.

The number of SAEs will be reported.

10.3.1.2. Statistical Evaluation of Safety

10.3.1.2.1. Injection-Site Pain

VAS pain score will be summarized using standard descriptive statistics. In addition, the severity of pain will be categorized by VAS pain score as: mild pain (\leq 30), moderate pain (\geq 30 and \leq 70), and severe pain (\geq 70). The number and percentage of the subjects in each pain severity category will be summarized by treatment and time point.

A mixed-effects repeated measures analysis model will be used to analyze the continuous injection-site pain VAS score by each time post-injection (0, 10, 20, 30, and 60 minutes). For measures at each time post-injection, the model will include treatment, period (Day 1, Day 8, or Day 15), treatment sequence, and treatment by treatment sequence as fixed effects. The covariance structure of the model will be unstructured. The Kenward-Roger method will be used to estimate the denominator degrees of freedom. Type III sums of squares for the least squares means will be used for the statistical comparison; treatment differences on every time point will be reported, along with the corresponding 95% confidence intervals for the differences. All pair-wise treatment comparisons by measuring time point will be evaluated and presented.

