Abnormal lab values will be listed. Other safety parameters that will be assessed include injection-site assessments, including pain, induration, swelling, pruritus, bleeding/bruising, and erythema/redness. The parameters will be listed, and summarized using standard descriptive statistics. Suicidal ideation and/or behavior and self-injurious behavior with no suicidal intent, based on the C-SSRS, will be listed by subject. HADS item scores will be listed for subjects with HADS depression subscale ≥ 11 at any time. Additional analyses may be performed if warranted upon review of the data.

VAS pain score will be summarized using standard descriptive statistics. In addition, the severity of pain will be categorized by VAS pain score as: mild pain (\leq 30), moderate pain (>30 and \leq 70), and severe pain (>70). The number and percentage of the subjects in each pain severity category will be summarized by treatment and time point.

2. Schedule of Activities

Study Schedule Protocol I1F-MC-RHCS

Study Schedu	Screening	-	Study Day											Comments
Procedure	-28 to -2 days prior to Day 1	Day -1	Day 1	Day 7	Day 8	Day 14	Day 15	Day 21 (± 1 day)	Days 28 & 35 (± 3 days)	Day 43 (± 3 days)	Days 50, 57, & 64 (± 3 days)	Day 71 (± 3 days)		
Informed Consent	X													
Subject Admission to CRU		X		X		X								
Subject Discharge from CRU			X		X		X							
Safety Assessment (Telephone Call)									X		X	X		Every effort will be made to contact subjects as near to this time as possible but missed calls will not be recorded as protocol deviations.
Medical History and Demographics	X													
Height	X													
Weight	X	X											X	
Serology	X													
QuantiFERON® -TB Gold or TST	X													
Randomization			X											

	Screening						Study Da	ay					FU/ ED ^a	Comments
Procedure	-28 to -2 days prior to Day 1	Day -1	Day 1	Day 7	Day 8	Day 14	Day 15	Day 21 (± 1 day)	Days 28 & 35 (± 3 days)	Day 43 (± 3 days)	Days 50, 57, & 64 (± 3 days)	Day 71 (± 3 days)		
Investigational Product Administration			X		X		X							
Ethanol Testing and Urine Drug Screen	X	X		X		X								May be repeated at the discretion of the investigator.
Pregnancy Test (Females Only; as applicable)	X	X		X		X							X	Serum pregnancy test will be performed at screening. Urine pregnancy test will be performed at all subsequent time points.
FSH Test	X													Females only, if applicable.

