 - ii. Either 1 highly-effective method of contraception (such as combination oral contraceptives, implanted contraceptives, or intrauterine device) or a combination of 2 effective methods (such as male or female condoms with spermicide, diaphragms with spermicide, or cervical sponges) will be used. The subject may choose to use a double-barrier method of contraception. Barrier protection methods without concomitant use of a spermicide are not a reliable or acceptable method. Thus, each barrier method must include use of a spermicide. It should be noted that the use of male and female condoms as a double-barrier method is not considered acceptable due to the high failure rate when these methods are combined.
- 3) Women not of child-bearing potential may participate and include those who are:
 - i. infertile due to surgical sterilization (hysterectomy, bilateral oophorectomy, bilateral salpingectomy, tubal ligation, or permanent tubal occlusion such as Essure), a congenital anomaly such as mullerian agenesis; or
 - ii. post-menopausal defined as either:
 - a) a woman at least 50 years of age with an intact uterus, not on hormone therapy, who has had either:
 - cessation of menses for at least 1 year; or
 - at least 6 months of spontaneous amenorrhea with a follicle-stimulating hormone level >40 mIU/mL.
 - b) a woman 55 years or older, not on hormone therapy, who has had at least 6 months of spontaneous amenorrhea;

- c) a woman 55 years or older with a diagnosis of menopause prior to starting hormone replacement therapy.
- [2] are aged at least 18 (20 for Japanese subjects) to 75 years at the time of screening.
- [3] have a body mass index (BMI) of 18.0 to 32.0 kg/m², inclusive at screening.
- [4] have venous access sufficient to allow for blood sampling as per the protocol.
- [5] are reliable and willing to make themselves available for the duration of the study and are willing to follow study procedures.
- [6] are able and willing to give informed consent.
- [7] For Japanese subjects, the subject, the subject's biological parents, and all of the subject's biological grandparents must be of exclusive Japanese descent and born in Japan.

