9.4.5.3. Injection-Site Pain

Pain measurements will be quantified using the 100-mm VAS pain score for all subjects. The VAS is a well-validated tool (Williamson and Hoggart 2005) to assess injection-site pain; it is presented as a 100-mm line anchored by verbal descriptors, usually "no pain" and "worst imaginable pain." The subject will be asked to relate any pain at the injection site on a scale of 1 to 100 mm on the line immediately (within 1 minute) following injection and at the time points listed in the Schedule of Activities (Section 2).

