Appendix 2. Clinical Laboratory Tests

Safety Laboratory Tests

Hematology

Hematocrit Hemoglobin

Erythrocyte count (RBC) Mean cell volume Mean cell hemoglobin

Mean cell hemoglobin concentration

Leukocytes (WBC)

Platelets

Differential WBC absolute counts of:

Neutrophils Lymphocytes Monocytes Eosinophils

Basophils

Urinalysis

Specific gravity

рН

Protein

Glucose Ketones

Bilirubin Urobilinogen

Blood

Nitrite
Microscopy (if dipstick abnormal)

c 1

Serology

Hepatitis B surface antigen^a Hepatitis B core antibody^a Hepatitis C antibody^a

HIV^a

Clinical Chemistry

Sodium Potassium Bicarbonate Chloride Calcium

Glucose (random)

Blood urea nitrogen (BUN)

Uric acid

Total cholesterol
Total protein
Albumin
Total bilirubin
Direct bilirubin
Triglycerides

Alkaline phosphatase (ALP) Aspartate aminotransferase (AST) Alanine aminotransferase (ALT)

Creatinine

Phosphorus

Other tests

Pregnancy test (females only, if applicable)^b

FSH (females only, if applicable)^{a, c} QuantiFERON $^{\mathbb{R}}$ -TB Gold or TST a

Ethanol testing^d Urine drug screen^d

Abbreviations: FSH = follicle-stimulating hormone; HIV = human immunodeficiency virus; RBC = red blood cells; TST = tuberculin skin test; WBC = white blood cells.

- a Performed at screening only
- b Serum pregnancy test to be performed at screening. Urine pregnancy test to be performed at all other times.
- c FSH test performed for women \geq 50 and \leq 55 years of age who have had spontaneous amenhorrhea for \geq 6 months but \leq 1 year to confirm non-childbearing potential (\geq 40 mIU/mL).

d Urine drug screen and ethanol level will be performed locally at screening and at admission to the clinical research unit. Test may be repeated at additional time points at the discretion of the investigator.

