#### 9.3.10 Injection Site Pain Assessment

Pain measurements will be quantified using the 100-mm VAS pain score (100-mm line anchored by verbal descriptors, usually "no pain" and "worst imaginable pain) for all subjects, whether or not they report injection pain.

Final, 8 January 2019 Page 8 of 10

VAS pain score will be summarized using standard descriptive statistics. In addition, the severity of pain will be categorized by VAS pain score as: mild pain ( $\leq$ 30), moderate pain ( $\geq$ 30 and  $\leq$ 70), and severe pain ( $\geq$ 70). The number and percentage of the subjects in each pain severity category will be summarized by formulation and time point. Figures of the continuous injection-site pain VAS score will also be presented, by formulation and measuring time point.

A mixed-effects repeated measures analysis model will be used to analyze the continuous injection-site pain VAS score by each time post-injection (0, 10, 20, 30, and 60 minutes). For measures at each time post-injection, the model will include formulation, period (Day 1, Day 8, or Day 15), formulation sequence, and formulation by formulation sequence as fixed effects. The covariance structure of the model will be unstructured. The Kenward-Roger method will be used to estimate the denominator degrees of freedom. Type III sums of squares for the least squares means will be used for the statistical comparison; formulation differences on every time point will be reported, along with the corresponding 95% confidence intervals for the differences. All pair-wise formulation comparisons by measuring time point will be evaluated and presented.

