# 12. CHANGES FROM THE PROTOCOL SPECIFIED STATISTICAL ANALYSES

There were no changes from the protocol specified statistical analyses.

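### Do the pain-severity categories, which as printed share the scores 30 and 70, need correcting before analysis?

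*Protocol*

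**What the plan says.** The pain categories are defined in three places.

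- Protocol synopsis, Statistical Analysis: "mild pain (\leq 30), moderate pain (>30 and \leq 70), and severe pain (>70".
- Protocol 10.3.1.2.1: mild is 30 or below, followed by "moderate pain (\geq 30 and \leq 70), and severe pain (\geq 70".
- SAP 9.3.10: the same limits as 10.3.1.2.1, ending with "\leq$ 70), and severe pain ( $\geq$ 70".

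In each place the categories serve one purpose: counts and percentages of subjects per category, by formulation and time point. Neither document adds a rule for scores that fall exactly on a limit.

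Two further SAP statements bear on which text applies. Section 3 gives the SAP precedence over the protocol's statistical text. Section 12 declares: "There were no changes from the protocol specified statistical analyses".

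The primary endpoint (protocol section 4) is the VAS score itself within 1 minute of injection. The mixed model in 10.3.1.2.1 and SAP 9.3.10 analyses that continuous score at 0, 10, 20, 30 and 60 minutes.

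**The concern.** Severity categories should place every score in exactly one class. With closed limits on both sides, 30 counts as both mild and moderate, and 70 as both moderate and severe. A program that follows the SAP to the letter would count such a subject twice, and the three percentages in a cell could add up to more than 100%. A program that allows one category per score would have to choose a side, and the SAP does not say which.

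The order of precedence seems to make this worse, because the SAP governs and the SAP carries the overlapping version. Its declaration of no changes does not help, because the protocol contains both versions. What would be at stake is the accuracy of a table that describes the study's main measurement, and one that may also be used in the interim review, which covers VAS data.

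**Working it through.** **1. The limits side by side**

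| Place | Mild | Moderate | Severe |
|---|---|---|---|
| Protocol synopsis | ≤30 | >30 and ≤70 | >70 |
| Protocol 10.3.1.2.1 | ≤30 | ≥30 and ≤70 | ≥70 |
| SAP 9.3.10 | ≤30 | ≥30 and ≤70 | ≥70 |

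The upper limits agree everywhere and are closed. Only the two lower limits differ, and only in the sign.

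**2. Each rule applied to every whole-millimetre score**

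Protocol 9.4.5.3 has subjects mark pain "on a scale of 1 to 100 mm on the line", so 30 and 70 are attainable scores.

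- Synopsis, scores 1 to 100: 30 + 40 + 30 = 100. Each score has one category.
- 10.3.1.2.1 and SAP 9.3.10, scores 1 to 100: 30 + 41 + 31 = 102 for 100 scores. Exactly two scores, 30 and 70, are shared.
- If the line starts at 0, the totals are 31 + 40 + 30 = 101 and 31 + 41 + 31 = 103 for 101 scores. The same two scores are shared.

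No version leaves a score unclassified. The overlap is in the text as supplied.

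**3. Is the sign reliable in this text?**

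The documents were machine-read from PDF. Protocol Appendix 2, footnote c, is a useful control because section 6.1 sets the same limits independently.

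- FSH level: the footnote has "to confirm non-childbearing potential (\geq 40 mIU/mL"; section 6.1 has "with a follicle-stimulating hormone level >40 mIU/mL".
- Age: the footnote prints ≤55 years, but section 6.1 already qualifies women of 55 or older with 6 months of amenorrhea, without FSH. A strict <55 would match.
- Duration: the footnote prints ≤1 year, but section 6.1 already qualifies women of at least 50 with at least 1 year without menses, again without FSH. A strict <1 year would match.

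All three differ from section 6.1 in the direction seen here: a strict sign appears as a non-strict one.

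**4. Size, for illustration only**

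The documents give no distribution of scores. Assume 78 subjects (the planned completers) and whole-millimetre scores spread evenly over the 101 values from 0 to 100.

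- Ratings on one boundary: 78 × 1/101 = 0.77. On both: 78 × 2/101 = 1.54.
- Sum of percentages under literal double counting: one boundary rating gives 79/78 = 101.3%; two give 80/78 = 102.6%.
- If one rating in ten is rounded to a multiple of 10 (11 such values): 0.9 × 2/101 + 0.1 × 2/11 = 3.6%, and 78 × 3.6% = 2.8. More rounding would give more, so this is not an upper bound.
- The amendment overview reports about 80% of VAS data collected when enrolment stopped. If that means 0.8 × 78, about 62 subjects, the even-spread figure is 62 × 2/101 = 1.2.
- If no score is exactly 30 or 70, the effect is zero.

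**5. What depends on the categories**

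Only the severity counts and percentages. The continuous summaries, the least squares mean differences and their 95% confidence intervals do not use them.

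**The case for a change.** The strongest opposing case has three parts.

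First, misreading is not automatic. Strict signs survive in the synopsis version of this very sentence and in the liver-test limits of protocol 8.1, and the overlap appears at both lower limits in two separate files. This stands to the extent that an artefact is plausible but not proven. It is weakened because the SAP text closely follows the protocol's, so one pattern of misreading could recur in both.

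Second, the SAP governs, so the overlapping version is what a programmer would work from. That is correct, and section 12 does not cure it. But a single derived severity variable gives each score one value, and the programmer has only one non-overlapping definition to turn to: the synopsis. It keeps the closed upper limits that the SAP itself prints. Table details are also left to the TFL shells named in SAP section 3, which are not available here and may already fix the boundary.

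Third, SAP 14.1 reports percentages as whole numbers, so a total of 101% could pass as rounding and hide a double count. This is fair for the percentages. The same table also gives counts, though, and counts that exceed the number of subjects cannot be explained by rounding. SAP 9.1 provides listings of all databased data, so the individual scores are there for a recount.

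**Conclusion.** The overlap exists in the text as extracted, but it does not establish an error in the plan, and no change is called for. Comparison strengthens the possibility of a misread sign: Appendix 2 shows the same shift at three limits, and the synopsis has the same sentence with strict signs. A look at the two source pages would settle it.

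If those pages do show closed limits on both sides, this is a clerical slip with an obvious reading. The synopsis supplies the only complete partition, it agrees with every printed upper limit, and an analyst would use it. Whichever side is chosen, the same rule applies to all three formulations, and only ratings of exactly 30 or 70 could move.

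Their number cannot be estimated from the documents. Under the stated assumptions (78 subjects, even spread, whole millimetres) it is about 1.5 per formulation and time point; it could be zero, or higher if subjects favour round numbers. None of this reaches the primary endpoint, the mixed model or any treatment comparison.

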10.3.1.2.2. Statistical Evaluation of Other Safety Parameters

Abnormal lab values will be listed. Other safety parameters that will be assessed include injection-site assessments, including pain, induration, swelling, pruritus, bleeding/bruising, and erythema/redness. The parameters will be listed and summarized using standard descriptive statistics. Suicidal ideation and/or behavior and self-injurious behavior with no suicidal intent, based on the C-SSRS, will be listed by subject. Only subjects that show suicidal ideation/behavior or self-injurious behavior without suicidal intent will be included in the listing (ie, if a subject answers are all 'no' for the C-SSRS, then that subject will not be displayed). HADS item scores will be listed for subjects with HADS depression sub-scale ≥11 at any time. Additional analyses may be performed if warranted upon review of the data.

10.3.2. Data Review During the Study

Data will be reviewed by the investigator and Sponsor throughout the course of the study to ensure subject safety.

Appendix 1. Abbreviations and Definitions

Term	Definition
AE	adverse event: Any untoward medical occurrence in a subject or clinical investigation subject administered a pharmaceutical product that does not necessarily have a causal relationship with this treatment. An AE can therefore be any unfavorable and unintended sign (including an abnormal laboratory finding), symptom, or disease temporally associated with the use of a medicinal (investigational) product, whether or not related to the medicinal (investigational) product.
ADA	antidrug antibodies
Al	autoinjector
ALP	alkaline phosphatase
ALT	alanine aminotransferase
AST	aspartate aminotransferase
BCG	Bacillus Calmette-Guérin
ВМІ	body mass index
CEC	Clinical Events Committee
CIOMS	Council for International Organizations of Medical Sciences
complaint	A complaint is any written, electronic, or oral communication that alleges deficiencies related to the identity, quality, purity, durability, reliability, safety or effectiveness, or performance of a drug or drug delivery system.
compliance	Adherence to all the study-related requirements, good clinical practice requirements, and the applicable regulatory requirements.
confirmation	A process used to confirm that laboratory test results meet the quality requirements defined by the laboratory generating the data and that Lilly is confident that results are accurate. Confirmation will either occur immediately after initial testing or will require that samples be held to be retested at some defined time point, depending on the steps required to obtain confirmed results.
СР	Clinical Pharmacologist
CRP	Clinical Research Physician: Individual responsible for the medical conduct of the study. Responsibilities of the CRP may be performed by a physician, clinical research scientist, global safety physician or other medical officer.
CRU	clinical research unit
C-SSRS	Columbia Suicide Severity Rating Scale
ECG	electrocardiogram
eCRF	electronic case report form

enroll The act of assigning a subject to a treatment. Subjects who are enrolled in the study are

those who have been assigned to a treatment.

Subjects entered into a study are those who sign the informed consent form directly or enter

through their legally acceptable representatives.

ERB ethical review board

GCP good clinical practice

HADS Hospital Anxiety and Depression Scale

HIV human immunodeficiency virus

ΙB Investigator's Brochure

IBD inflammatory bowel disease

ICF informed consent form

ICH International Council for Harmonisation

lg immunoglobulin

IL interleukin

IND Investigational New Drug: An application to the FDA to allow testing of a new drug in

humans.

informed consent A process by which a subject voluntarily confirms his or her willingness to participate in a

> particular study, after having been informed of all aspects of the study that are relevant to the subject's decision to participate. Informed consent is documented by means of a

written, signed and dated informed consent form.

interim analysis An interim analysis is an analysis of clinical study data, separated into treatment groups,

that is conducted before the final reporting database is created/locked.

Investigational product (IP)

A pharmaceutical form of an active ingredient or placebo being tested or used as a reference in a clinical study, including products already on the market when used or assembled

(formulated or packaged) in a way different from the authorized form, or marketed products used for an unauthorized indication, or marketed products used to gain further information

about the authorized form.

investigator A person responsible for the conduct of the clinical study at a study site. If a study is

conducted by a team of individuals at a study site, the investigator is the responsible leader

of the team and may be called the principal investigator.

ISR injection-site reaction

I۷ intravenous

Legal

An individual or judicial or other body authorized under applicable law to consent, on Representative behalf of a prospective subject, to the subject's participation in the clinical study.

MTD maximum tolerated dose

PFS prefilled syringe

Ps psoriasis

Q2W every 2 weeks

Q4W every 4 weeks

randomize the process of assigning subjects to an experimental group on a random basis

RBC red blood cell

SAE serious adverse event

SC Subcutaneous(ly)

screen The act of determining if an individual meets minimum requirements to become part of a

pool of potential candidates for participation in a clinical study.

SUSARs suspected unexpected serious adverse reactions

TB tuberculosis

TBL total bilirubin level

TEAE treatment-emergent adverse event: Any untoward medical occurrence that emerges during

a defined treatment period, having been absent pretreatment, or worsens relative to the pretreatment state, and does not necessarily have to have a causal relationship with this

treatment

TST tuberculosis skin test

ULN upper limit of normal

VAS visual analogue scale

WBC white blood cell

